### **6.2.2. Treatment assessments (week 2 +/-3 days)**

The following procedures/assessments are to be completed at the end of Week 2.

- Perform a detailed medical history
- Assessment of AEs and concomitant medications
- Pregnancy prevention counseling and confirmation of contraception
- Obtain body height and weight
- Obtain vital signs (resting blood pressure, pulse and temperature)
- Perform complete physical examination, including vasculitis, joint, neuropathy examination and sicca syndrome (for subjects with Sicca syndrome)
- Vasculitis activity score (Birmingham vasculitis score) for subjects with vasculitis.
- Glomerulonephritis evaluation (urine sample and serum creatinine sample) for subjects with glomerulonephritis
- ACR20-70 score (for subjects with Rheumatoid arthritis). This score includes a physical exam, a HAQ and a blood sample to evaluate ESR or CRP.
- Obtain blood samples for:
  - Hematology profile
  - Chemistry profile

- Analysis of cryoglobulinemia measuring cryoglobulins, analyzing cross reactive idiotypes, analysis of complement and HCV core ELISA.
- Obtain urine sample for:
  - Urinalysis and urine creatinine
- Subject completes Health Assessment Questionnaire
- Review study drug compliance and drug administration instructions with subject

### **6.2.3. Treatment assessments (week 4+/-7 days)**

- Perform a detailed medical history
- Assessment of AEs and concomitant medications
- Pregnancy prevention counseling and confirmation of contraception
- Obtain body height and weight
- Obtain vital signs (resting blood pressure, pulse and temperature)
- Vasculitis activity score (Birmingham vasculitis score) for subjects with vasculitis.
- Glomerulonephritis evaluation (urine sample and serum creatinine sample) for subjects with glomerulonephritis
- ACR20-70 score (for subjects with Rheumatoid arthritis). This score includes a physical exam, a HAQ and a blood sample to evaluate ESR or CRP.
- Perform complete physical examination, including vasculitis, joint, neuropathy examination and sicca syndrome (for subjects with Sicca syndrome)
- Obtain blood samples for:
  - Hematology profile
  - Chemistry profile
  - Coagulation profile
  - HCV RNA
  - ESR and CRP
  - Analysis of cryoglobulinemia measuring cryoglobulins, analyzing cross reactive idiotypes, analysis of complement, HCV core ELISA and FACS
- Obtain urine sample for:
  - Urine pregnancy test for females of childbearing potential only
  - Urinalysis and urine creatinine
- Subject completes Health Assessment Questionnaire

- Review study drug compliance and drug administration instructions with subject
- Drug Administration:
  - Dispense study drug
  - Review study drug compliance

**6.2.4. Treatment assessments (week 8+/-7 days and week 20+/-7 for those subjects on Harvoni 24 weeks)**

- Perform a detailed medical history
- Assessment of AEs and concomitant medications
- Pregnancy prevention counseling and confirmation of contraception
- Obtain body height and weight
- Obtain vital signs (resting blood pressure, pulse and temperature)
- Vasculitis activity score (Birmingham vasculitis score) for subjects with vasculitis.
- Glomerulonephritis evaluation (urine sample and serum creatinine sample) for subjects with glomerulonephritis
- ACR20-70 score (for subjects with Rheumatoid arthritis). This score includes a physical exam, a HAQ and a blood sample to evaluate ESR or CRP.
- Perform complete physical examination, including vasculitis, joint, neuropathy examination and sicca syndrome (for subjects with Sicca syndrome)
- Obtain blood samples for:
  - Hematology profile
  - Chemistry profile
  - Coagulation profile
  - ESR and CRP
  - HCV RNA
- Analysis of cryoglobulinemia measuring cryoglobulins, analyzing cross reactive idiotypes, analysis of complement and HCV core ELISA
- Obtain urine sample for:
  - Urine pregnancy test for females of childbearing potential only
  - Urinalysis and urine creatinine
- Subject completes Health Assessment Questionnaire
- Review study drug compliance and drug administration instructions with subject

- Review study drug compliance

#### **6.2.5. End of treatment (week 12 or week 24 +/-7 days)**

The following procedures/assessments are to be completed at the end of treatment(week 12 or week 24, depending on treatment arm):

- Perform a detailed medical history
- Assessment of AEs and concomitant medications
- Pregnancy prevention counseling and confirmation of contraception
- Obtain body height and weight
- Obtain vital signs (resting blood pressure, pulse and temperature)
- Vasculitis activity score (Birmingham vasculitis score) for subjects with vasculitis.
- Glomerulonephritis evaluation (urine sample and serum creatinine sample) for subjects with glomerulonephritis
- ACR20-70 score (for subjects with Rheumatoid arthritis). This score includes a physical exam, a HAQ and a blood sample to evaluate ESR or CRP.
- Perform complete physical examination, including vasculitis, joint, neuropathy examination and sicca syndrome (for subjects with Sicca syndrome)
- Subject completes Health Assessment Questionnaire
- Obtain blood samples for:
  - Hematology profile
  - Chemistry profile
  - Coagulation profile
  - HCV RNA
  - ESR and CRP
  - Analysis of cryoglobulinemia measuring cryoglobulins, analyzing cross reactive idiotypes, analysis of complement, HCV core ELISA and Clonality/Lymphoproliferation / FACS
- Obtain urine sample for:
  - Urine pregnancy test for females of childbearing potential only
  - Urinalysis and urine creatinine
- Complete medication pill count.

### **6.3. Post-treatment assessments**

The post treatment Week 4, 12 and 24 visits should be timed from the date of last administration of study drugs.

#### **6.3.1. Post Treatment Week 4 (+/- 7 days)**

The following procedures/assessments are to be completed for all subjects, 4 weeks after taking the last dose of study drugs:

- Perform a detailed medical history
- Assessment of AEs and concomitant medications
- Pregnancy prevention counseling
- Obtain body height and weight
- Obtain vital signs (resting blood pressure, pulse and temperature)
- Vasculitis activity score (Birmingham vasculitis score) for subjects with vasculitis.
- Glomerulonephritis evaluation (urine sample and serum creatinine sample) for subjects with glomerulonephritis
- ACR20-70 score (for subjects with Rheumatoid arthritis). This score includes a physical exam, a HAQ and a blood sample to evaluate ESR or CRP.
- Perform complete physical examination, including vasculitis, joint, neuropathy examination and sicca syndrome (for subjects with Sicca syndrome)
- Subject completes Health Assessment Questionnaire
- Obtain blood samples for:
  - Hematology profile
  - Chemistry profile
  - Coagulation profile
  - ESR and CRP
  - HCV RNA
  - Analysis of cryoglobulinemia measuring cryoglobulins, analyzing cross reactive idiotypes, analysis of complement, HCV core ELISA and FACS.
- Obtain urine sample for:
  - Urine pregnancy test
  - If a positive urine pregnancy test is reported, the subject will be asked to return to the clinic for a confirmatory serum pregnancy test.
  - Urinalysis and urine creatinine

### **6.3.2. Post Treatment Week 12 and 24 (+/- 7 days)**

The following procedures/assessments are to be completed for the post treatment Week 12 and 24 Visits:

- Perform a detailed medical history
- Assessment of SAEs and concomitant medications
- Obtain body height and weight
- Obtain vital signs (resting blood pressure, pulse and temperature)
- Vasculitis activity score (Birmingham vasculitis score) for subjects with vasculitis.
- Glomerulonephritis evaluation (urine sample and serum creatinine sample) for subjects with glomerulonephritis
- ACR20-70 score (for subjects with Rheumatoid arthritis). This score includes a physical exam, a HAQ and a blood sample to evaluate ESR or CRP.
- Perform complete physical examination, including vasculitis, joint and neuropathy examination.
- Sicca evaluation: evaluation by medical history and physical examination (for subjects with Sicca syndrome).
  - Sicca evaluation: evaluation of xerostomia (saliva from Stensen's duct) and xerophthalmia (Schirmer tests) will be performed at PT week 24.
- For those subjects with neuropathy associated to cryoglobulinemia: A complete neurological examination will be performed (Mount Sinai Hospital Department of Neurology) will be performed at Post treatment week 24.
- Obtain blood samples for:
  - Hematology profile
  - Chemistry profile
  - Coagulation profile
  - ESR and CRP
  - HCV RNA
  - Analysis of cryoglobulinemia measuring cryoglobulins, analyzing cross reactive idiotypes, analysis of complement, HCV core ELISA and clonality/lymphoproliferation / FACS.
- Obtain urine sample for:

- urinalysis and urine creatinine
- Subject completes Health Assessment Questionnaire

#### **6.4. Procedures and Specifications**

Fasting is not required for any of the procedures except for Fibroscan that requires 6 hour fasting.

##### **6.4.1. Clinical Laboratory Analytes**

- Hematology profile: Hematocrit, Hemoglobin (Hb), Platelet count, Red blood cell count (RBC), White blood cell count (WBC) with differential (absolute and percentage) including Lymphocytes, Monocytes, Neutrophils, Eosinophils, Basophils, Reticulocyte count and MCV. These studies will be performed at Core Laboratory at Mount Sinai Hospital.
- Coagulation profile: INR, Prothrombin time (PT), Activated partial thromboplastin time (APTT). These studies will be performed at Core Laboratory at Mount Sinai Hospital.
- Chemistry profile: Alanine aminotransferase (ALT/SGPT), Aspartate aminotransferase (AST/SGOT), Albumin, Alkaline phosphatase, Creatine Kinase, Creatinine, Total Bilirubin (reflex to Direct Bilirubin), Glucose, Lipase, Potassium, Sodium; Fibrotest® /APRI calculation, and Direct Bilirubin at Screening only. These studies will be performed at Core Laboratory at Mount Sinai Hospital.
- Urinalysis: Appearance, Blood, Color, Glucose, Leukocyte esterase, pH, Protein, Urobilinogen. These studies will be performed at Core Laboratory at Mount Sinai Hospital.
- Urine creatinine level. This study will be performed at Core Laboratory at Mount Sinai Hospital.
- Virological Tests: Serologies for HCV, HBV and HIV. HCV RNA will be measured using the COBAS® TaqMan® HCV Test, v2.0 for use with Ampliprep. HCV genotype and subtype will be determined using the Siemens VERSANT® HCV Genotype INNO-LiPA 2.0 Assay. These studies will be performed at Core Laboratory at Mount Sinai Hospital.

- IL28B genotype will be determined by polymerase chain reaction (PCR) amplification of the SNP, rs12979860, with sequence specific forward and reverse primers and allele specific fluorescently labeled TaqMan® MGB probes. These studies will be performed at Core Laboratory at Mount Sinai Hospital.
- Pregnancy Tests: Serum  $\beta$ -hCG or Urine  $\beta$ -hCG.

#### **6.4.2. Medical History**

Medical history including details regarding illnesses and allergies, date(s) of onset, and whether condition(s) is currently ongoing, and medication history, including prior HCV treatment history (only applicable for treatment experienced subjects), will be collected on all subjects during screening.

Obtain HCV treatment history as per Section 4.2.

Obtain MC treatment history as per Section 4.2.

#### **6.4.3. Complete Physical Examination**

A complete physical examination will include source documentation of general appearance, and the following body systems: Head: eyes, ears, nose, throat, mouth and tongue; Neck Range of motion (ROM, thyroid, cervical nodes Chest: (excluding breasts); respiratory; Cardiovascular: heart rate and rhythm, murmurs and gallops Lymph nodes: axillary, inguinal Abdomen: tenderness, organomegaly Skin: rashes, hair, nails Joints: tenderness, ROM, heat, swelling Musculoskeletal: muscle strength and tenderness Neurological. Physical examination will also include evaluation of the amount of saliva and tear production by visual inspection of the salivary and lacrimal glands.

#### **6.4.4. Vital Signs**

Assessment of vital signs will include measurement of resting blood pressure, pulse, respiratory rate, and temperature.

Blood pressure will be measured using the following standardized process:

- Subject should sit for  $\geq 5$  minutes with feet flat on the floor and measurement arm supported so that the midpoint of the manometer cuff is at heart level;
- Use a mercury sphygmomanometer or automatic blood pressure device with an appropriately sized cuff with the bladder centered over the brachial artery;

- Measure and record the blood pressure to the nearest 2 mmHg mark on the manometer or to the nearest whole number on an automatic device.

#### **6.4.5. Creatinine Clearance (CLcr)**

Creatinine clearance is calculated by the Cockcroft-Gault equation {2202} using actual body weight (BW).

$$\text{Male: CLcr (mL/min)} = [140 - \text{age (years)}] \times \text{BW(kg)} / 72 \times \text{Scr}$$

$$\text{Female: CLcr (mL/min)} = [140 - \text{age (years)}] \times \text{BW(kg)} \times 0.85 / 72 \times \text{Scr}$$

Scr = serum creatinine (mg/dL)

#### **6.4.6. 12-Lead ECGs**

Subjects will be required to rest in a supine position for  $\geq 5$  minutes prior to making a recording.

The investigator (or qualified designee) should review the ECG traces recorded in real time for clinically significant abnormalities.

#### **6.4.7. Viral RNA Sequencing / Phenotyping Sample**

Plasma samples will be collected at Baseline/Day 1 and each visit thereafter for viral sequence analysis. At any unscheduled visit initiated for the purpose of confirming virologic breakthrough, a viral sequence analysis plasma sample must be collected.

#### **6.4.8. Pregnancy Testing**

All females of childbearing potential will have urine pregnancy testing every 4 weeks during the dosing period and 30 days after last dose of study drug.

Definition of childbearing potential is described in Appendix 3.

If a positive urine pregnancy test is reported, the subject will be asked to return to the clinic for a confirmatory serum pregnancy test.

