### **3. STUDY DESIGN**

#### **3.1. Treatment plan and regimen**

This is a single-center, open-label study to evaluate the safety, tolerability and efficacy of new direct acting oral antivirals:

- Ledipasvir/Sofosbuvir 90mg/400 mg FDC (LDV/SOF;Harvoni®, for those subjects enrolled under protocol version 1 only) in patients with genotype 1 HCV infection and MC already enrolled in protocol version 1 or
- Sofosbuvir/Velpatasvir 400mg/100mg FDC (SOF/VEL; Epclusa®, for all subjects enrolled under protocol version 2) in patients with chronic genotypes 1-6 HCV infection and MC. All subjects enrolled in protocol version 2 will receive Epclusa® who have failed or only partially responded to other MC therapies.

Treatment duration is as follows:

Subjects that have been already enrolled and started treatment under protocol version 1 will continue and complete the planned treatment with LDV/SOF FDC (Harvoni®):

- Treatment naïve subjects will be treated for 12 weeks.
- Treatment experienced non-cirrhotic subjects will be treated for 12 weeks.
- Treatment experienced compensated cirrhotic subjects will be treated for 24 weeks.

Subjects enrolled under protocol version 2 will receive SOF/VEL FDC (Epclusa®):

- Treatment-naïve subjects will be treated for 12 weeks
- Treatment-experienced non-cirrhotic subjects will be treated for 12 weeks
- Treatment-experienced compensated cirrhotic subjects will be treated for 12 weeks

Approximately 20% of subjects may have cirrhosis.

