#### **3.2. Visits schedule**

All subjects will complete screening, on-treatment, and post treatment assessments.

Screening assessments will be completed within 30 days of the Baseline/Day 1 visit, 42 days if liver biopsy is required.

All subjects will complete the following study visits: Screening, Baseline/Day 1, on-treatment visits at Weeks 2, 4, 8 and 12 (for all patients) and weeks 20 and 24 (for those patients receiving 24 weeks of Harvoni® treatment).

Visits	Screening	Baseline / Day 1	Week 2	Week 4	Week 8	Week 12	Week 20	Week 24
12 weeks (Harvoni® or Epclusa®) treatment arm	X	X	X	X	X	X		
24 weeks (Harvoni®) treatment arm	X	X	X	X	X	X	X	X

All subjects will complete post treatment Week 4, 12 and 24 visits.

The assessments performed at each visit are described in Section 6 and shown in Appendix 1.

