#### **4.3. Exclusion criteria**

1. Chronic liver disease of a non-HCV etiology (e.g., alcoholic liver disease, hepatotoxic drug exposure, autoimmune hepatitis hemochromatosis, Wilson's disease, alfa-1 antitrypsin deficiency, cholangitis).
2. Infection with hepatitis B virus (HBV) or human immunodeficiency virus (HIV).
3. Patients with cirrhosis and Child-Pugh class B or C (Child-Pugh score will be calculated using laboratory parameters from screening visit).
4. Current or prior history of any of the following:
  - 4.1. Clinically-significant illness (other than HCV) or any other major medical disorder that in the opinion of the Investigator may interfere with subject treatment, assessment or compliance with the protocol; subjects currently under evaluation for a potentially clinically-significant illness (other than HCV) are also excluded.
5. Difficulty with blood collection and/or poor venous access for the purposes of phlebotomy.

6. Clinical hepatic decompensation (i.e. ascites, encephalopathy or variceal hemorrhage).
7. Solid organ transplantation.
8. Clinically significant pulmonary disease, cardiac disease or psychiatric disease that in the opinion of the investigator renders the subject a poor risk for inclusion into the study.
9. Malignancy within the 5 years prior to screening, with the exception of specific cancers that have been cured by surgical resection (basal cell skin cancer, etc). Subjects under evaluation for possible malignancy are not eligible.
10. Significant drug allergy (such as anaphylaxis or hepatotoxicity).
11. Pregnant (serum pregnancy test to be performed for all women of childbearing potential at screening and urine pregnancy test at baseline); nursing female or unwillingness to practice birth control. Patients are expected to maintain adequate birth control to prevent pregnancy for 30 days post-completion of the drug (appendix 3).
12. Known hypersensitivity to SOF, VEL or formulation excipients.
13. Participation in an investigational trial of a drug or device (excluding observational studies) within 30 days prior to screening and through the duration of study participation.

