## 6. STUDY PROCEDURES

Study visits will occur at Screening, Baseline/Day 1, and on-treatment at Weeks 2, 4, 8, and 12 (weeks 20 and 24 for 24 weeks treatment period subjects). Post treatment Visits will occur at Weeks 4, 12, and 24 following the last dose of study medications.

Information on the specific laboratory parameters to be measured and clinical assessments to be performed are described below and in **Appendix 1**.

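### The pregnancy test rule in Section 6.4.8 does not match the visit schedule: an 8-week gap on the 24-week Harvoni course, and a post-treatment window that allows the last test before day 30

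*Combined protocol and SAP*

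**What the plan says.** **The rule.** Section 6.4.8 covers all females of childbearing potential and requires "urine pregnancy testing every 4 weeks during the dosing period and 30 days after last dose of study drug". It makes no exception for course length.

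**Course length.** Section 3.1 gives 24 weeks of dosing to one group only, under Harvoni (version 1): "Treatment experienced compensated cirrhotic subjects will be treated for 24 weeks". The corresponding Epclusa (version 2) group has 12 weeks: "Treatment-experienced compensated cirrhotic subjects will be treated for 12 weeks". All other subjects on either drug also have 12 weeks.

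**On-treatment visits.** Section 3.2 sets visits at Weeks 2, 4, 8 and 12 for everyone and adds "weeks 20 and 24 (for those patients receiving 24 weeks of Harvoni® treatment"). The synopsis and the opening of Section 6 give the same list. Urine pregnancy tests are listed at Day 1 (6.2.1), Week 4 (6.2.3), Weeks 8 and 20 (6.2.4) and end of treatment, meaning Week 12 or Week 24 by arm (6.2.5). The Week 2 list (6.2.2) has none.

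**Post-treatment visits.** Section 6.3 times these from the last dose. Section 6.3.1 lists a urine pregnancy test at Week 4, with a window of 7 days either side. Section 6.3.2 (Weeks 12 and 24) lists none. The synopsis names urine pregnancy tests among the post-treatment assessments without tying them to a visit.

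**Contraception period.** Exclusion criterion 11 in Section 4.3 states: "Patients are expected to maintain adequate birth control to prevent pregnancy for 30 days post-completion of the drug".

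**Early terminators.** Sections 3.3, 3.5 and 3.6 send them to an early termination visit and then to post-treatment Weeks 12 and 24, without naming Week 4. Sections 3.2 and 6.3.1 say that all subjects attend Week 4.

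**The concern.** Section 6.4.8 is a safety rule, and the visit lists are what the site will follow. Where the two disagree, a subject can attend every visit on time and still breach the rule, so the schedule itself creates deviations.

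Detection matters because other parts of the protocol depend on it. Section 3.5 makes pregnancy a reason for mandatory discontinuation of study drug, and Section 8.4.1.2.1 requires pregnancies to be reported. Dosing continues through the gap on the 24-week course: Section 5.2.2 dispenses two bottles at Week 12 and none at Week 20.

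**Working it through.** The plan gives no figure to reproduce. The check is date arithmetic on visits whose procedure list includes a pregnancy test.

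**Inputs.** Test visits and windows come from Sections 6.2.1 to 6.2.5 and 6.3.1. Day 1 has no window; the others allow 7 days either side. The target interval is 4 × 7 = 28 days (Section 6.4.8).

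**Formula.** For consecutive test visits at weeks a and b, the nominal gap is 7 × (b − a) days. The shortest and longest gaps subtract or add the two windows.

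| Schedule | Interval | Nominal (days) | Range with windows (days) |
|---|---|---|---|
| Both | Day 1 to Week 4 | 28 | 21 to 35 |
| Both | Week 4 to 8 | 28 | 14 to 42 |
| Both | Week 8 to 12 | 28 | 14 to 42 |
| 24-week only | Week 12 to 20 | 7 × 8 = 56 | 56 − 14 = 42 to 56 + 14 = 70 |
| 24-week only | Week 20 to 24 | 28 | 14 to 42 |

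The 12-week schedule is 4-weekly at nominal dates. On the 24-week schedule, the Week 12 to 20 interval is twice the stated one, and even its shortest permitted length (42 days) exceeds 28.

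**Two assumptions in the Week 12 to 20 row.** Section 6.2.5 ties its list and window to end of treatment, by arm. No separate Week 12 list is given for 24-week subjects. The row assumes that both the test and the window apply to them at Week 12. If no test is done then, the gap runs from Week 8 to Week 20: 7 × 12 = 84 days (84 − 14 = 70 to 84 + 14 = 98).

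**Post-treatment test.** Week 4 is day 28, and the window is 28 − 7 = day 21 to 28 + 7 = day 35, or 15 permitted days. Day 30 is inside it. Days 21 to 29 (9 of 15) fall before day 30; days 30 to 35 (6 of 15) do not. The nominal date is 30 − 28 = 2 days early, and the earliest permitted date is 30 − 21 = 9 days early. Because the contraception period is also 30 days, the last test listed in Section 6.3 can come up to 9 days before that period ends.

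**Early terminators.** If Week 4 is omitted, the next visit is post-treatment Week 12, day 84 ± 7 (days 77 to 91), and Section 6.3.2 lists no test there. Section 3.6 refers to Section 6.2.7 for the early termination visit, but Section 6.2 ends at 6.2.5, so the text does not show whether that visit includes a test.

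**Number affected on the 24-week course.** The documents do not give it. Ten subjects with about 20% cirrhotic gives 10 × 0.20 = 2. Those on the 24-week course must also be treatment-experienced and enrolled under version 1, and only women of childbearing potential count. I assume 0 to about 2.

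**The case against.** - **The schedule works for most subjects.** A reader might infer that the visit schedule cannot meet the rule at all. It can for every Epclusa subject and for all Harvoni groups but one, whose tests are 4-weekly at nominal dates. This objection stands.
- **Day 30 is achievable.** A reader might also infer that the 30-day test is impossible. Day 30 lies inside the window, so this objection stands too. The 28-versus-30 difference may be ordinary rounding: Section 8.3 uses 4 weeks for adverse events and Section 5.4 uses 30 days for concomitant medications. The 2 nominal days alone are trivial. What remains is that the window opens on day 21, so a compliant visit need not satisfy the rule.
- **Week 4 may not be the only post-treatment test.** The synopsis does not limit post-treatment urine tests to one visit, so it would be too strong to say that Weeks 12 and 24 certainly have none. Section 6.3.2 omits them, however, so the two places need reconciling.
- **Tests might be done between visits.** Section 6.4.8 asks a woman with a positive result to return to the clinic, which could suggest testing elsewhere. That is weak evidence, because Section 6.3.1 gives the same instruction for a test listed at a clinic visit. No section provides for tests between visits.
- **The appendices are not visible.** Section 6 points to Appendix 1, and Appendix 3 covers pregnancy precautions. Neither is in the text available for review, so an additional test there cannot be excluded. Sections 3.2 and 6 would then still need to agree with it.
- **The consequence is limited.** Contraception is counselled and confirmed at on-treatment visits, and pregnancies are reported throughout follow-up. A reader might infer that pregnancies would go undetected; the documents support only a longer possible delay.

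**Conclusion.** The point holds as a minor internal contradiction in two places.

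1. On the 24-week Harvoni course, the scheduled visits leave 56 days between tests against a stated 28. The range is 42 to 70 days if the windows apply at Week 12. The gap is 84 days if Week 12 carries no test for this group.
2. For all women of childbearing potential, the post-treatment Week 4 window includes day 30 but does not guarantee a test on or after it. The synopsis and Section 6.3.2 differ on later tests, and Sections 3.3, 3.5 and 3.6 differ from Sections 3.2 and 6.3.1 on whether early terminators attend Week 4.

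The documents do not support a general failure of the schedule. The conclusion rests on the body text alone, with Appendices 1 and 3 unseen, and on the absence of any provision for tests between visits. The efficacy analyses are not affected.

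**What to change.** Reconcile the synopsis, Sections 3.2, 3.3, 3.5, 3.6, the opening visit list of Section 6, Sections 6.2.5, 6.3.1, 6.3.2 and 6.4.8, and Appendices 1 and 3, so that the test rule and the visits or windows agree. Four things need stating:

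- how the rule in Section 6.4.8 applies between Weeks 12 and 20 on the 24-week course, and whether Week 12 carries a test for that group;
- how the 30-day test relates to the post-treatment Week 4 window;
- which post-treatment visits include a test;
- which visits early terminators attend and which of them include a test, with the reference to Section 6.2.7 corrected.

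Which interval or window applies is for the investigators.

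The cost is wording or a window change. If the written 4-week interval is kept, the 8-week gap means one additional urine test per affected woman (8 / 4 − 1 = 1), for a handful of women at most and possibly none. If Week 12 turns out to carry no test for that group, its list would need settling as well.
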